1.2.3 BRAF and MEK Inhibitors as Combination Therapy

Clinical evaluation of the dabrafenib 150 mg BID + trametinib 2 mg QD (150/2) combination treatment has shown efficacy in patients with V600 mutant melanoma. The results of the randomized Part C of Study BRF113220 in BRAF-inhibitor naïve subjects demonstrated an improved efficacy profile for the 150/2 combination treatment compared to dabrafenib monotherapy across all efficacy parameters tested.

BRF113220 was a Phase I/II study with 4 parts that include a randomized part (Part C) which investigated the clinical activity, durability of response, safety/tolerability and population PK parameters in the three different arms in subjects with BRAF-mutant melanoma ($n = 162$). In Part C, a statistically significant ($p = 0.0264$) increase in the confirmed overall response rate was observed in the 150/2 treatment arm (76%) when compared to the dabrafenib monotherapy arm (54%) [Flaherty KT 2012b]. Moreover, the rate of complete responses was higher in the 150/2-treatment arm (9% vs 4%) while early disease progression (i.e., no best response of disease progression (PD) at the first timepoint assessment), was absent (0 vs 6%) when compared to the dabrafenib monotherapy arm. Clinically more important, the investigator-assessed PFS was significantly prolonged for the 150/2 combination arm relative to the dabrafenib monotherapy arm ($HR = 0.39$; $p < 0.0001$) [Flaherty KT 2012b]. This benefit was sustained at 12 months, with a 12-month progression-free rate of 41% in the 150/2 arm vs 9% in the dabrafenib monotherapy arm. While a significant difference in PFS was also observed in the 150/1 combination therapy group compared to dabrafenib monotherapy ($HR = 0.56$, $p = 0.0057$), the benefit was lower at 12 months (12-month progression-free rate of 26%) [Flaherty KT 2012b].

Safety data reported from Part C showed that dose-limiting toxic effects were infrequently observed in subjects receiving combination therapy with 150 mg of dabrafenib and 2 mg of trametinib (combination 150/2). Cutaneous squamous-cell carcinoma was seen in 7% of subjects receiving combination 150/2 and in 19% receiving dabrafenib monotherapy ($p = 0.09$), whereas pyrexia was more common in the combination 150/2 group than in the monotherapy group (71% vs. 26%) [Flaherty KT 2012b].

MEK115306 study is a double blind randomized phase III study that recruited 423 previously untreated metastatic melanoma patients who had BRF V600E or V600K mutation. Eligible patients were randomized to receive dabrafenib 150mg bid plus trametinib 2mg qd, or dabrafenib 150mg bid plus placebo. The primary endpoint was PFS. The results showed the combination significantly improved PFS (median PFS: 9.3 vs 8.8 months, HR=0.75, $p=0.03$) and response rate (67% vs 51%, $p=0.0002$). The interim OS analysis at 6 months showed the survival rate was 93% and 85% in the combination arm vs dabrafenib arm (HR=0.63, $p=0.02$). However, a pre-defined specific efficacy stopping boundary of OS (two-side $p=0.00028$) was crossed. So the survival follow-up is still on-going as of December 2014.

In this study, 9% patient from combination treatment arm and 5% from dabrafenib monotherapy arm permanently discontinued study medication before disease progression. In addition, dose reduction was required in 25% and 13% of patients receiving combination and dabrafenib monotherapy, respectively.

The adverse event profile of combination treatment was different from dabrafenib monotherapy. The patients who received combined treatment experienced more frequent pyrexia(51% vs 28%), chill(30% vs 16%), diarrhea(24% vs 14%), hypertension(22% vs 14%), vomiting(20% vs 14%), peripheral edema(14% vs 5%), elevated ALT (11% vs 5%) or AST (11% vs 3%), decreased left ventricular ejection fraction(LVEF)(4% vs 2%), dermatitis acneiform(8% vs 3%), but less frequent cutaneous squamous-cell carcinoma(2% vs 9%), hyperkeratosis(3% vs 32%), skin papilloma(1% vs 21%), hand-foot syndrome(5% vs 27%), dry skin(9% vs 13%), pruritus(8% vs 12%) and alopecia(7% vs 26%). [Long GV 2014]

MEK116513 study is an open label randomized phase III study that recruited 704 previously untreated metastatic melanoma patients who had BRF V600E or V600K mutation. Eligible patients were randomized to receive dabrafenib 150mg bid plus trametinib 2mg qd, or vemurafenib 960mg bid. The primary endpoint was overall survival. At a pre-planned interim analysis, this study demonstrated the combination of dabrafenib plus trametinib achieved significant OS improvement (12 months OS rate: 72% vs 65%, HR: 0.69, $p=0.005$) and this result crossed the pre-defined interim stopping boundary. Therefore this study was stopped because of the efficacy and the interim analysis was considered the final analysis. The combination treatment also significantly improved PFS (median PFS: 11.4 vs 7.3 months, HR: 0.56, $p<0.001$) and response rate (64% vs 51%, $p<0.001$).

Rates of study-drug discontinuations were similar in the two groups(13% in combination arm and 12% in vemurafenib arm). Adverse events leading to dose reduction was reported in 33% of patients in combination arm and 39% in the vemurafenib arm.

The most frequent adverse events in the combination-therapy group were pyrexia (53%), nausea (35%), diarrhea (32%), chills (31%), fatigue (29%), headache (29%), and vomiting (29%). In the vemurafenib group, the most frequent adverse events were arthralgia (51%), rash (43%), alopecia (39%), diarrhea (38%), nausea (36%), and fatigue (33%). Skin toxic effects were more frequent in the vemurafenib group than in the combination-therapy group,

in particular rash (43% vs. 22%), photosensitivity reaction (22% vs. 4%), hand–foot syndrome (25% vs. 4%), skin papillomas (23% vs. 2%), squamous-cell carcinomas and keratoacanthomas (18% vs. 1%), and hyperkeratosis (25% vs. 4%). Pyrexia was more frequent in the combination-therapy group than in the vemurafenib group (53% vs. 21%). Grade 3 or 4 adverse events occurred in 52% of the patients in the combination-therapy group and in 63% of those in the vemurafenib group. Three fatal events occurred in each group; all were deemed by the investigator to be unrelated to the study drug [Robert C 2015].

1.2.3.1 Dabrafenib and Trametinib in Acral Lentiginous Melanoma

Acral lentiginous melanoma is one of 4 major histological subtypes of cutaneous melanoma. It is characterized by lesions presenting on non-hair bearing skin including the palm, soles, and nail beds. Although ALM accounts for only 2% to 3% of all melanomas in Caucasians, ALM makes up a much higher proportion (40-50%) of cutaneous malignant melanomas in darker-skinned individuals (ie, blacks, Asians, and Hispanics) [Bradford PT 2009]. The frequency of BRAF mutations in melanoma varies with anatomical site and sun exposure patterns. BRAF mutations are less frequent (25 – 30%) in acral melanoma not associated with chronic sun-damage [Curtin JA 2006] [Curtin JA 2006]. In contrast, c-Kit mutations are more common in mucosal (39%) and acral melanomas (36%), which can also be accompanied by an increase in c-Kit copy numbers [Curtin JA 2006]. Thus far, very few patients with ALM have been treated with dabrafenib and trametinib combination since the vast majority subjects enrolled were Caucasians.

To date, approximately 14 subjects with acral lentiginous melanoma have been treated with dabrafenib or trametinib monotherapy, or combination therapy with both agents. In the dabrafenib BREAK-3(BRF113683) study, 5 subjects with ALM received dabrafenib either in the randomized study or after crossover. Exposure to dabrafenib ranged from 3 days (subject discontinued treatment due to adverse event) to 5 months. In addition, one subject with ALM was enrolled into the METRIC (MEK114267) study with trametinib monotherapy and was treated with trametinib for over 50 weeks.

In the BRF113220 study, 8 subjects received combination dabrafenib and trametinib therapy either in the randomized phase or after crossover from dabrafenib monotherapy. Exposure time ranged from 3 to 18 months, including 2 subjects with a partial response who are still ongoing on study treatment.

In Asian population, approximately 25.5% of all melanoma patients and 15.5% of ALM have BRAF V600 mutation [Lu S 2011]. There are no PK data in Chinese patients. Preliminary PK data obtained in Japanese patients showed there no major ethnic difference in the pharmacokinetic profile of trametinib or dabrafenib when administered in monotherapy [GlaxoSmithKline Document Number 2014N196180_00 and GlaxoSmithKline Document Number 2012N133089_00], however, exposure to dabrafenib and trametinib tended to be higher when administered in combination [GlaxoSmithKline Document Number 2014N196181_00].

[figure not shown]
Data in subjects with acral lentiginous melanoma subtype or Asian population was limited and further exploration in these populations is warranted. This study was originally intended to enroll subjects with acral lentiginous melanoma. The eligibility criterion has been amended to include cutaneous melanoma in light of the advance in the management of metastatic melanoma with BRAF V600 mutation.

[figure not shown]
1.3 Rationale

[figure not shown]
- Clinical studies for dabrafenib and trametinib monotherapies have demonstrated single-agent clinical activity in subjects with BRAF-V600-mutant melanoma.
- Preclinical studies and clinical data indicate that primary- and acquired resistance to a BRAF-inhibitor single-agent therapy may be addressed and potentially overcome by a combination of a BRAF- and MEK-inhibitor
- Data from the BRF113220 study (Part C) and 2 randomized phase III study evaluating the combination of dabrafenib and trametinib demonstrated promising clinical activity and an acceptable clinical safety profile of the dabrafenib and trametinib combination given at full single-agent dose
- Limited data are available in non-Caucasian populations and ALM.
- Limited pharmacokinetic data are available from Asian subjects, in whom melanoma subtypes such as ALM may be more prevalent compared to Caucasian subjects.

[figure not shown]
1.4 Benefit: Risk Assessment

Summaries of findings from both clinical and non-clinical studies conducted with dabrafenib and trametinib can be found in the Investigator's Brochure [GlaxoSmithKline Document Number [2011N126811_02](#)]. The following section outlines the risk assessment and mitigation strategy for this protocol:

1.4.1 Benefit Assessment

Current research suggests that combination therapies of BRAF- and MEK-targeted agents can further improve the effect on survival currently achieved with BRAF inhibitor monotherapy [Long GV 2014; Robert C 2015] in metastatic melanoma patients with BRAF V600 mutation. Patients treated with combination of trametinib and dabrafenib can achieve a 6 months survival rate of 93% [Long GV 2014] and 12 months survival rate of 72% [Robert C 2015].

New treatments, like CTLA-4 antibody or anti-PD-1 antibodies, are not available in countries like China. Dacarbazine (DTIC), considered the most active of the agents currently available, is approved for metastatic melanoma [Huncharek M 2001] and widely used in clinical practice in Asian countries. The benefit of DTIC remains small, with median progression-free survival lasting approximately 2 months and median overall survival of approximately 7 months.

There are no PK data in Chinese patients. Preliminary PK data obtained in Japanese patients showed there no major ethnic difference in the pharmacokinetic profile of trametinib or dabrafenib when administered in monotherapy [GlaxoSmithKline Document Number 2014N196180_00 and GlaxoSmithKline Document Number 2012N133089_00], however, exposure to dabrafenib and trametinib tended to be higher when administered in combination [GlaxoSmithKline Document Number 2014N196181_00]. Nevertheless, the planned dose of study medication is expected to be tolerable in the study population and bring clinical benefit. Subjects enrolled into this study may benefit from receiving a combination of targeted agents which have demonstrated efficacy and tolerability in Caucasian populations.

1.4.2 Overall Benefit: Risk Conclusion

To date, >3000 subjects, of predominantly Caucasian ethnicity and with majority of BRAF V600 mutated melanoma have received this combination regimen in 5 phase I/II studies and 3 phase III studies. The complete list of these studies can be found in the IB.

As both agents target the MAP-kinase (MAPK) pathway, which is constitutively activated in V600 BRAF-mutation positive melanoma, a concomitant combination regimen may result in a more pronounced and prolonged anti-tumor efficacy as experimental data strongly suggests. This additive or synergistic activity is the result of a near-complete MAPK-pathway inhibition which addresses molecular mechanisms of primary resistance and delays the onset of secondary resistance to monotherapy treatment. Furthermore, in a relevant pre-clinical model of chemically induced skin carcinogenesis, inhibition of the MAPK-pathway at the two separate nodes of BRAF and downstream MEK abolished the paradoxical MAPK pathway activation induced by the BRAF inhibitor vemurafenib and resulted in an almost complete inhibition of cutaneous squamous cell carcinoma (cuSCC) development which is, a known side effect of monotherapy BRAF inhibition.

The safety profile for the combination treatment of dabrafenib 150 mg twice daily and trametinib 2 mg once daily in subjects with unresectable or metastatic melanoma with a BRAF V600 mutation is defined by the results of the pivotal Phase III Study MEK115306 and MEK116513 and supported by the BR113220 pooled combination therapy population [GlaxoSmithKline Document Number 2011N126811_02].

The combination therapy has a higher rate of pyrexia, fatigue and nausea, while lower incidences of hyperkeratosis, alopecia and skin papilloma were observed compared with dabrafenib monotherapy. Relative to trametinib monotherapy, there was a higher incidence of fatigue, nausea, and vomiting observed but lower incidences of rash and diarrhea with combination therapy.

Overall, the addition of dabrafenib to trametinib does not appear to increase the frequency or severity of cardiac-related AEs, hypertension, hepatic disorders, diarrhea and pneumonitis, which previously were observed with trametinib monotherapy.

Similarly, the addition of trametinib to dabrafenib does not appear to increase the frequency or severity of palmar-plantar-erythrodysesthesia syndrome (PPES) or treatment-emergent malignancies previously observed with dabrafenib monotherapy.

The risk-to-benefit ratio in this patient population remains favorable.

[figure not shown]
2 OBJECTIVE(S) and endpoints

Table 1 lists the study objectives and corresponding endpoints.

Table 1 Study Objectives and Endpoints

Objectives	Endpoints
Primary	

 To determine the objective response rate (ORR) of dabrafenib in combination with trametinib in subjects with BRAF V600 mutation-positive, unresectable or metastatic acral lentiginous or cutaneous melanoma 	
 ORR defined as the percentage of subjects with evidence of a confirmed complete response (CR) or partial response (PR) as per RECIST v1.1 [Eisenhauer EA 2009].
Secondary	

 To further evaluate the antitumor activity (progression-free survival (PFS), duration of response, and overall survival (OS)) 	
 Duration of response is defined as the time from first documented evidence of CR or PR until the earliest date of documented radiological progression or death due to any cause among subjects who achieved a confirmed CR or PR. PFS defined as the time from first dose of study treatment until the first date of either objective disease progression or death due to any cause. OS defined as the interval from first dose of study treatment to the date of death, irrespective of the cause of death; subjects still alive will be censored at the date of the last contact.

 To assess exposures to dabrafenib, dabrafenib metabolites, and trametinib after a single dose (Chinese patients) and at steady- 	
 Trametinib, dabrafenib and dabrafenib metabolites concentrations by visit. Noncompartmental PK parameters include

Objectives	Endpoints
state, and characterize the population pharmacokinetics and pharmacodynamics of dabrafenib and trametinib	trametinib, dabrafenib and dabrafenib metabolites C _{max} , t _{max} , C _{trough} , AUC(0-t), and AUC(0-8); AUC(0-12) (dabrafenib and dabrafenib metabolites only), AUC (0-24) (trametinib only) and the dabrafenib metabolite to dabrafenib ratio of AUC(0-12). For Chinese patients, the accumulation ratio will be calculated by using the pharmacokinetic parameters from Day 1 and Day 15. Population PK parameters include, apparent clearance following oral dosing (CL/F), volume of distribution (V/F), and absorption rate constant (K _a) for dabrafenib and trametinib.

To evaluate the safety and tolerability of dabrafenib and trametinib	
Safety as measured by clinical assessments including vital signs and physical examinations, 12-lead electrocardiograms (ECG), echocardiogram (ECHO), eye exams, chemistry and hematology laboratory values, and adverse events (AEs).

3 Study design

3.1 Study Design

Protocol waivers or exemptions are not allowed. Therefore, adherence to the study design requirements, including those specified in the Time and Events Table, are essential and required for study conduct.

This is an open-label, Phase IIA, multi-center study to evaluate the objective response rate of dabrafenib and trametinib combination therapy in subjects that have BRAF V600 mutation-positive ALM or cutaneous melanoma. Approximately 65 subjects will be enrolled to receive oral dabrafenib 150 mg twice daily in combination with oral trametinib 2 mg once daily.

Dose modification guidelines for adverse events are provided in Section 5.8. Other measures of efficacy including duration of response, PFS and OS, as well as PK and PD properties, safety and tolerability of dabrafenib and trametinib will also be evaluated. Blood and tissue samples will be collected to determine possible mechanisms of drug response and resistance. Subjects will continue study treatment until disease progression, death, unacceptable toxicity, withdrawal of consent, or study completion. After treatment discontinuation, subjects will be followed for survival and disease progression as applicable.

The study completion is defined as:

- In case all subjects stop study treatment within 48 weeks after Last Subject First Visit(LSFV): the study is completed once the last subject has completed the 48 weeks survival follow-up or all subjects die or loss to follow-up, whichever comes first.
- In case some subjects are still on study treatment 48 weeks after LSFV: the study is completed once all subjects stop study medication, or all subjects who are still on study medication can have access to alternative supply of MEK/BRAF inhibitors, whichever comes first.

Supplementary study conduct information not mandated to be present in this protocol is provided in the accompanying Study Procedures Manual (SPM). The SPM will provide the site personnel with administrative and detailed technical information that does not impact subject safety.

4 Subject selection and discontinuation/completion criteria

4.1 Subject Selection Criteria

4.1.1 Number of Subjects

Approximately 65 subjects will be enrolled. See Section 9.2.1 for sample size assumptions.

4.1.2 Inclusion Criteria

Specific information regarding warnings, precautions, contraindications, adverse events, and other pertinent information on the Novartis investigational product or other study treatment that may impact subject eligibility is provided in the trametinib and dabrafenib and trametinib combination IB's.

Deviations from inclusion criteria are not allowed because they can potentially jeopardize the scientific integrity of the study, regulatory acceptability or subject safety. Therefore, adherence to the criteria as specified in the protocol is essential.

Subjects eligible for enrolment in the study must meet all of the following criteria:

1. Signed written informed consent, which includes compliance with the requirements and restrictions listed in the consent form.
2. ≥ 18 years of age,
3. Histologically confirmed acral lentiginous or cutaneous melanoma that is either Stage IIIC (unresectable) or Stage IV (metastatic), and determined to be BRAF V600 mutation-positive by a central reference laboratory. Subjects with ocular or mucosal melanoma are not eligible.
4. Measurable disease (i.e., present with at least one measurable lesion) by RECIST version 1.1 [Eisenhauer EA 2009] by investigator's assessment. Refer to Section 7.2.3 for the definition of a measurable lesion.
5. Performance status score of 0 or 1 according to the Eastern Cooperative Oncology Group (ECOG) scale [Oken MM 1982].
6. All prior anti-cancer treatment-related toxicities (except alopecia and laboratory values as listed on Table 2) must be \leq Grade 1 according to the Common Terminology Criteria for Adverse Events version 4 (CTCAE version 4.0) at the time of enrolment [NCI 2009].
7. Able to swallow and retain oral medication and must not have any clinically significant gastrointestinal abnormalities that may alter absorption such as malabsorption syndrome or major resection of the stomach or bowels.
8. Women of child-bearing potential (see Section 7.3.7 for definitions) must have a negative serum pregnancy test within 14 days of first dose of study treatment and agree to use effective contraception, as stated in Section 7.3.7 from 14 days prior to enrolment, throughout the treatment period and for 4 months after the last dose of study treatment.
9. Adequate baseline organ function as defined in Table 2.
10. Subjects with East Asian origin.

Table 2 Definitions for Adequate Baseline Organ Function

System	Laboratory Values
Hematologic^a	
ANC	$\geq 1.2 \times 10^9/L$
Hemoglobin	$\geq 9 \text{ g/dL}$
Platelet count	$\geq 100 \times 10^9/L$
PT/INR ^b and PTT	$\leq 1.5 \times \text{ULN}$
Hepatic	
Albumin	$\geq 2.5 \text{ g/dL}$
Total bilirubin	$\leq 1.5 \times \text{ULN}^c$
AST and ALT	$\leq 2.5 \times \text{ULN}$

Renal	
Calculated creatinine clearance ^d	≥ 50 mL/min
Cardiac	
Left Ventricular Ejection Fraction (LVEF) ^e	≥ LLN by ECHO

ANC=absolute neutrophil count, PT=prothrombin time, INR=international normalized ratio, PTT=partial thromboplastin time, AST=aspartate aminotransferase, ALT=alanine aminotransferase, LLN=lower limit of normal

- a. Laboratory values obtained without growth factors or transfusion support for at least 4 weeks
- b. Subjects receiving anticoagulation treatment may be allowed to participate with INR established within the therapeutic range prior to enrollment.
- c. Total bilirubin < 1.5 x ULN except for patients with Gilbert's syndrome who may only be included if total bilirubin < 3.0 x ULN or direct bilirubin < 1.5 x ULN.
- d. Calculate creatinine clearance using standard Cockcroft-Gault formula ([Appendix 2](#)).
- e. ECHO scans must be used throughout the study.

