5.2 Dosage and Administration

- Dabrafenib, 150 mg, BID;
- Trametinib, 2.0 mg, once daily.

When administered in combination with trametinib, take the once-daily dose of trametinib at approximately the same time each day with either the morning dose or the evening dose of dabrafenib. The second dose of dabrafenib (150 mg) should be administered approximately 12 hours after the morning dose. Study medication should be taken orally with approximately 200 mL of water under fasting conditions, either 1 hour before or 2 hours after a meal.

If a subject vomits after taking study medication, the subject should be instructed not to retake the dose and should take the next dose as originally scheduled.

If administration of trametinib is interrupted or permanently discontinued, administration of dabrafenib may be continued. If administration of dabrafenib is interrupted, or permanently discontinued, administration of trametinib may continue.

If a subject misses a dose of dabrafenib, the subject may take the dose immediately if the next dose is scheduled for at least 6 hours later. If the next scheduled dose of dabrafenib is due in less than 6 hours, the subject should skip the dose and resume of dabrafenib dosing at the next scheduled dose

If a subject misses a trametinib dose, the subject may take the dose immediately if the next dose is scheduled for at least 12 hours later.

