7.3.7 Pregnancy Testing, Prevention and Reporting

7.3.7.1 Pregnancy Testing and Prevention

The need for a screening pregnancy test depends on whether a female subject is of childbearing potential or non-childbearing potential.

A female of non-childbearing potential (i.e., physiologically incapable of becoming pregnant) is defined as any female who has had a hysterectomy, bilateral oophorectomy (ovariectomy) or bilateral tubal ligation, or is post-menopausal.

A practical definition accepts menopause after 1 year without menses with an appropriate clinical profile, e.g., age appropriate, >45 years in the absence of hormone-replacement therapy (HRT). In questionable cases, the subject must have a follicle-stimulating hormone (FSH) value >40 mIU/mL and an estradiol value <40 pg/mL (<140 pmol/L).

A female of child-bearing potential is defined as any female who does not meet the criteria of non-childbearing potential as described in the previous paragraph.

If a female subject is of childbearing potential, she must have a serum β -human chorionic gonadotropin (HCG) pregnancy test performed within 14 days of first dose of study treatment. Subjects with a positive pregnancy test result must be excluded from the study. Subjects with a negative pregnancy test result must agree to use an effective contraception method as described below throughout the treatment period and for 16 weeks after stopping treatment with trametinib or 2 weeks after stopping treatment with dabrafenib monotherapy, whichever is longer.

Novartis-acceptable contraceptive methods, when used consistently and in accordance with both the product label and the instructions of the physician, are as follows:

- Placement of a hormonal or non-hormonal intrauterine device (IUD) or intrauterine system (IUS) with a documented failure rate of less than 1% per year.
- Sterilization (at least 6 months prior to screening) for male partners. The vasectomized male partner should be the sole partner for that subject.
- Total abstinence (when in line with the preferred and usual lifestyle of the subject). Periodic abstinence (e.g. calendar, ovulation, symptothermal, post-ovulation methods), and withdrawal are not acceptable methods of contraception.

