2.1.3.4 Time unit

A year length is defined as 365.25 days. A month length is 30.4375 days (365.25/12). If duration is reported in months, duration in days will be divided by 30.4375. If duration is reported in years, duration in days will be divided by 365.25.

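### Inclusion criterion 8 and Protocol Section 7.3.7.1 set different post-treatment contraception periods: about 10 days apart if both drugs stop together, at most about 108 days apart if dabrafenib continues alone

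*Protocol*

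**What the plan says.** Inclusion criterion 8 (Protocol Section 4.1.2) asks women of child-bearing potential to "agree to use effective contraception, as stated in Section 7.3.7 from 14 days prior to enrolment", and then to continue during treatment and "for 4 months after the last dose of study treatment". It gives one duration and counts it from one date.

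Section 7.3.7.1, which is the section that criterion 8 points to, sets the period "for 16 weeks after stopping treatment with trametinib or 2 weeks after stopping treatment with dabrafenib monotherapy, whichever is longer". It gives two durations, each counted from the stop of a different drug, and the longer applies.

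Three other places bear on how the two texts interact:

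- The opening of Section 5 says that study treatment can mean either drug or the pair.
- Section 5.2 says: "If administration of trametinib is interrupted or permanently discontinued, administration of dabrafenib may be continued". Section 5.8.1 likewise lets a subject stay on dabrafenib when trametinib can be reduced no further.
- In Section 5.8.3.1, Table 6 with its footnotes has trametinib stopped for good after a symptomatic LVEF decrease, and allows a restart of dabrafenib alone to be considered.

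**The concern.** Criterion 8 presents itself as an application of Section 7.3.7 but differs from it in both duration and reference date. A woman whose site works from the eligibility page and a woman whose site works from the pregnancy section could be told different things about the same period after treatment. The protocol regards pregnancy in that period as a risk to be prevented. It also says that deviations from inclusion criteria are not allowed, so a site that applies only the shorter text is at odds with a criterion that it may not relax. What is at stake is subject safety and compliance with the protocol, not the efficacy estimate.

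**Working it through.** **Inputs**

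- Criterion 8: 4 months from the last dose of study treatment, read here as the last dose of whichever drug stops later.
- Section 7.3.7.1: 16 weeks = 16 × 7 = 112 days from stopping trametinib; 2 weeks = 14 days from stopping dabrafenib monotherapy; the later end date governs.
- Month length, used only for conversion: SAP Section 2.1.3.4 gives 365.25/12 = 30.4375 days. The protocol has no conversion of its own for this purpose.

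The documents give no figure for the difference, so there is none to reproduce.

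**Step 1: criterion 8 in days.** 4 × 30.4375 = 121.75 days. Counted on the calendar, four months is 120 to 123 days.

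**Step 2: both drugs stop on the same day.** Section 7.3.7.1 gives 112 days. Difference: 121.75 − 112 = 9.75 days (8 to 11 by calendar).

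**Step 3: dabrafenib continues alone.** Let g be the number of days from the last trametinib dose to the last dabrafenib dose. Counted from the last dabrafenib dose, Section 7.3.7.1 requires max(112 − g, 14) days, and criterion 8 still requires 121.75. The difference is 121.75 − max(112 − g, 14).

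| g (days on dabrafenib alone) | Section 7.3.7.1 (days) | Criterion 8 (days) | Difference (days) |
|---|---|---|---|
| 0 | 112 | 121.75 | 9.75 |
| 28 | 84 | 121.75 | 37.75 |
| 56 | 56 | 121.75 | 65.75 |
| 98 | 14 | 121.75 | 107.75 |
| 200 | 14 | 121.75 | 107.75 |

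The 2-week branch takes over when 112 − g = 14, that is at g = 98 days (14 weeks). From there the difference stays at 121.75 − 14 = 107.75 days (106 to 109 by calendar).

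**Step 4: dabrafenib stops first and trametinib continues.** Both texts then count from the last trametinib dose, and the difference is again 9.75 days.

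**Step 5: direction.** Criterion 8 is the longer requirement in every case above. Even its shortest calendar value, 120 days, exceeds 112. A site that applies criterion 8 therefore also satisfies Section 7.3.7.1, and the reverse is not true.

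**The case against.** The strongest reply is that little turns on this. For a woman who stops both drugs together, 4 months against 16 weeks is close to a rounding difference. One of the two texts already satisfies both. The large difference needs a woman of child-bearing potential, among about 65 subjects, who gives up trametinib and then takes dabrafenib alone for at least 14 weeks. The protocol permits that course, but the documents give no count of such women.

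Timing also limits the effect. Criterion 8 is an agreement made at entry. According to the amendment log, the 2-week period dates from Amendment 7 (15-Feb-2019), about a year after the primary analysis cut-off of 23-Feb-2018, by which point SAP Section 1.1 indicates that enrolment was complete.

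Most of this stands, and it is why the severity is low. It does not remove the point. Criterion 8 imposes an obligation that runs after treatment, so it outlasts enrolment. Both texts are in the current protocol (Amendment 8, 27-Nov-2019), and the last visit was on 19-Apr-2021, so they stood together while the study was running.

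A reader might infer more than the documents support:

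- **That sites following either text would breach the other.** Step 5 shows that the shortfall runs one way only.
- **That a flat 2-week rule applies after dabrafenib.** The later end date governs, so the 2 weeks decide the matter only after 98 days or more on dabrafenib alone.
- **That the dabrafenib-alone case is bound to arise.** The wording is permissive; it can arise.
- **That women were in fact told different things.** Women are instructed through the consent form and site materials, which are not available here. The protocol text could lead to different instructions; whether it did cannot be judged.

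**Conclusion.** The inconsistency is real and lies in current text. Its usual size is about 10 days, and its conditional maximum is about 108 days, reached when trametinib stopped at least 98 days before the last dabrafenib dose. A site relying on Section 7.3.7.1 alone would fall short of criterion 8; a site relying on criterion 8 would meet both.

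This rests on three readings: the SAP month length for conversion (the calendar range moves each figure by no more than 2 days), the last dose of study treatment taken as the last dose of either drug, and the rule in Section 7.3.7.1 taken as the later of two end dates.

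The point is an internal inconsistency of low severity. It does not touch the ORR analysis or the sample size. It concerns women of child-bearing potential only; the requirement for male subjects is stated separately.

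**What to change.** Reconcile inclusion criterion 8 and Section 7.3.7.1 so that both state the same post-treatment requirement and the same reference date or dates, and carry the reconciled text into the site instructions. Which duration applies, and whether the rule is single or drug-specific, is for the sponsor's clinical and safety staff to decide; nothing here favours one.

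The cost is about one sentence of protocol text plus the matching site instruction. No analysis changes. As the last visit has passed, the remaining value is in the study record and in any protocol that reuses this wording.
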